Visit Identifier Abbreviations used in this table may be found in Appendix 17	Screening	Treatment Period									EOT	4-week Follow- up	90-day Follow- up for irAEs	Notes
		Cycle 1 =28 days				Cycle ≥ 2 (28 days)								
Study Day	-28 to -1	1	2 ^a	8	15	16 ^a	22	1	8 ^b	15				
 Additional visit window may be allowed after discussion and agreement between investigator and sponsor. 
a: End of inpatient observation (PK, ECG, vital signs).
 
b: This D8 visit is only applicable for Cycles 2 and 3, whereas, C3D8 is applicable for PK/PD and ECG only.

Visit Window (days)		± 2		± 2	± 2			± 2	± 2	± 2		± 7	± 7	
Study Intervention														
PF-07260437		X (priming dose)		(X ^c)	X			X		X				
 C1D1 is priming dose and C1D15 is full/maintenance dose. c: A 2-step priming may be considered on C1D1 and C1D8. See Section 4.1 for additional information.

Table 3. Study Schedule of Assessments – Part 1 With Priming

Visit Identifier Abbreviations used in this table may be found in Appendix 17	Screening	Treatment Period									EOT	4-week Follow- up	90-day Follow- up for irAEs	Notes
		Cycle 1 =28 days												
Study Day	-28 to -1	1	2 ^a	8	15	16 ^a	22	1	8 ^b	15				
 Additional visit window may be allowed after discussion and agreement between investigator and sponsor.
Visit Window (days)		±2	±2	±2		±2	±2	±2	±2	±2		±7	±7	
a: End of inpatient observation (PK, ECG, vital signs).
 
b: This D8 visit is only applicable for Cycles 2 and 3, whereas, C3D8 is applicable for PK/PD and ECG only.

Premedication		(X)	(X ^d)	(X)			(X)		(X)					
 Prophylactic premedication is not allowed during the DLT evaluation period during initial dose escalation. However, if the participant experiences an infusion related reaction (IV), allergic reaction, significant injection site reaction, CRS, fever/chills, allergic reaction, nausea/vomiting, hypotension, or pain, appropriate treatment should initiate and premedication as prophylaxis may be considered for subsequent injections as well as for new participants. See Section 6.1.1.1 for additional information. d: Only applicable to 2-step priming

Table 3. Study Schedule of Assessments – Part 1 With Priming

Visit Identifier Abbreviations used in this table may be found in Appendix 17	Screening	Treatment Period									EOT	4-week Follow- up	90-day Follow- up for irAEs	Notes

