- **Priming Dose:** A priming dose approach in the next dose level may be initiated if a dose level induces \geq Grade 2 CRS (lasting for >24 hours) occurs in >1 participant despite treatment with tocilizumab and/or vasopressors. Initially, a single priming dose may be administered on C1D1 at 1 dose level below the dose level in which the recurrent \geq Grade 2 CRS event was observed. The first full dose will be administered on C1D15 with a starting full dose that is not higher than the full dose at which the recurrent \geq Grade 2 CRS event occurred. Depending on the observed safety and tolerability profile, dose escalation of the full dose may proceed with full dose increased by a maximum of 200%. If \geq Grade 2 CRS is observed after the administration of full doses, a 2 (or more) step-up priming dose approach may also be implemented (for example, 2 priming doses administered on C1D1 and C1D8, respectively); the initial priming dose will be at a dose level where predicted probability of \geq Grade 2 CRS is $<20\%$. In addition, dose finding without priming may still continue in parallel if MTD without priming has not been reached and RDE without priming has not been determined. Finally, additional priming dose strategies (eg, additional doses, different dosing levels and intervals) may be investigated based on emerging data.

All Part 1 participants in cohorts without a priming dose will be observed inpatient for at least 48 hours after the first SC dose (or the first IV dose, as applicable) on C1D1 and for at least 8 hours after the second SC dose (or the second IV dose, as applicable) on C1D15. Participants in cohorts with a priming dose will be observed inpatient for at least 24 hours after the first SC priming dose (or the first IV priming dose administration, as applicable) on C1D1 and 24 hours after the second (full) dose on C1D15 ([Table 7](#)). Modification of inpatient observation period might be allowed based on emerging safety data and will require discussion and agreement between investigator and sponsor.

- Participants who experience Grade ≥ 3 infusion-related adverse events (IV administration) or clinically significant cytokine release syndrome must be hospitalized for at least 24 hours for at least 4 doses subsequently (two cycles). If subsequent doses are tolerated without recurrence of Grade ≥ 3 infusion-related adverse events or clinically significant cytokine release syndrome, outpatient PF-

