4.3.2. Justification for Priming Dose Regimen

Priming dose approaches are commonly applied for T-cell engager bispecific modalities to initially sensitize the immune system at lower doses to reduce rate and grade of CRS ([Costa et al, 2019](#); [Garfall, 2020](#); [Madduri et al, 2020](#); [BLINCYTO \(blinatumomab\), 2021](#)). A priming dose approach may be initiated if a dose level induces \geq Grade 2 CRS (lasting for >24 hours) occurs in >1 participant despite treatment with tocilizumab and/or vasopressors. Initially, a single priming dose will be administered on C1D1 at 1 dose level below the dose level whereby the \geq Grade 2 CRS event was observed. The first full dose will be administered on C1D15 with a starting full dose that is 100% higher than the priming dose. Depending on the observed safety and tolerability profile, dose escalation on the full dose may still proceed with up to 3-fold increment from current full dose level. If \geq Grade 2 CRS is observed after the administration of full doses, a 2 step-up priming doses approach may also be implemented with the 2 priming doses administered on C1D1 and C1D8, respectively; both priming doses will be at dose levels where predicted probability of \geq Grade 2 CRS is $<20\%$.

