9.3.3. Secondary Endpoint Analysis

Part 1 and Part 2

Single-Dose and Steady-State PF-07260437 Pharmacokinetic Analysis

Serum concentrations of PF-07260437 will be summarized descriptively (n, mean, standard deviation, coefficient of variation, median, minimum, maximum, geometric mean, and its associated coefficient of variation) by dose, cycle, day, and nominal time.

Individual participant serum concentration-time data within a dose interval after Cycle 1 Day 1 and Cycle 2 Day 1 will be analyzed using noncompartmental methods to determine single and multiple dose PK parameters.

Single dose PK parameters to be estimated will include the serum C_{max} , T_{max} and AUC_{last} , and as data permit, AUC from time 0 extrapolated to infinity (AUC_{inf}), $t_{1/2}$, clearance (CL/F for SC dosing and CL for IV dosing) and volume (V_z/F for SC dosing and V_{ss} for IV dosing).

Multiple dose PK parameters to be estimated will include $C_{max,ss}$, $T_{max,ss}$, $AUC_{ss,t}$, $C_{min,ss}$, clearance (CL_{ss}/F for SC and CL_{ss} for IV) and as data permit, volume (V_z/F for SC or V_{ss} for IV), $t_{1/2}$, and R_{ac} ($AUC_{ss,t}/AUC_{sd,t}$). The single dose and steady-state PK parameters will be summarized descriptively (n, mean, standard deviation, coefficient of variation, median, minimum, maximum, geometric mean, and its associated coefficient of variation) by dose level and cycle.

Dose normalized AUC_{inf} (AUC_{τ} at steady state) and C_{max} will be plotted against dose (using a logarithmic scale) by cycle. These plots will include individual participant values and the geometric means for each dose.

Analysis of Immunogenicity Data

For the immunogenicity data, the percentage of participants with positive ADA and neutralizing antibodies each will be summarized. For participants with positive ADA or neutralizing antibodies, the magnitude (titer), time of onset, and duration of ADA or neutralizing antibodies response will also be described, if data permit.

Part 2

Efficacy Analysis

Response Evaluable Set will be used for all response-related analyses including ORR, DoR, PFS, and TTP (RECIST). Tumor response will be presented in the form of participant data listings that include, but are not limited to tumor type, tumor response at each visit, and best overall response. OS will be reported on the Full Analysis Set as well as on the mITT.

Data will be summarized (also graphically where appropriate) and listed by expansion cohort.

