10.17. Appendix 17: Abbreviations

The following is a list of abbreviations that may be used in the protocol

Abbreviation	Term
2L+	after first line standard of care
ACTH	adrenocorticotropic hormone
ADA	antidrug antibodies
ADL	activities of daily living
AE	adverse event
AHA	American Heart Association
AIDS	acquired immunodeficiency syndrome
ALP	alkaline phosphatase
ALT	alanine aminotransferase
ANC	absolute neutrophil count
aPTT	activated partial thromboplastin time
ASCO	American Society of Clinical Oncology
AST	aspartate aminotransferase
ASTCT	American Society for Transplantation and Cellular Therapy
AT	aminotransferases
AUC	area under the curve
AUC _{inf}	area under the concentration-time versus time curve from time 0 to infinity
AUC _{last}	area under the concentration-time curve from time 0 to time of last measurable concentration
AUC _{sd,τ}	area under the concentration-time curve after single dose over dosing interval τ
AUC _{ss,τ}	area under the concentration-time curve at steady state over dosing interval τ
AV	atrioventricular
B	B cells
BBS	Biospecimen Banking System
BiPAP	bilevel positive airway pressure
BLRM	Bayesian logistic regression model
BNP	brain natriuretic peptide
BP	blood pressure
Bpm	beats per minute
BrCa	breast cancer
BUN	blood urea nitrogen
BVN	bivariate normal
C	cycle
CAR	chimeric antibody receptor
CD3	Cluster-Defined 3
CDC	The Centers for Disease Control and Prevention

Abbreviation	Term
CDK	cyclin-dependent kinase
CFR	Code of Federal Regulations
CHF	congestive heart failure
CI	confidence interval
CIOMS	Council for International Organizations of Medical Sciences
CISH	chromogenic in situ hybridization
CK	creatine kinase
CK-MB	creatine kinase-muscle type, myocardial band
CL	clearance
CL/F	apparent clearance
CL _{ss} /F	apparent clearance at steady state
CLIA	Clinical Laboratory Improvement Amendments
C _{max}	maximum observed concentration
C _{max,ss}	maximum concentration at steady state
C _{min,ss}	minimum concentration at steady state
CNS	central nervous system
CO ₂	carbon dioxide
CONSORT	Consolidated Standards of Reporting Trials
COVID-19	coronavirus disease 2019
CPAP	continuous positive airway pressure
CR	complete response
CrCl	creatinine clearance
CRF	case report form
CRO	contract research organization
CRP	c-reactive protein
CRS	cytokine release syndrome
CSF	cerebral spinal fluid
CSR	clinical study report
CT	clinical trial/ computed tomography
CTCAE	Common Terminology Criteria for Adverse Events

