### Appendix 3 Abbreviations

The following is a list of abbreviations that may be used in the SAP.

Abbreviation	Term
AE	adverse event
ASTCT	American society for transplantation and cellular therapy
AUC	area under the concentration-time curve
AUC inf	area under the concentration-time versus time curve from time 0 to infinity

Abbreviation	Term
AUC last	area under the concentration-time curve from time 0 to time of last measurable concentration
AUC tau,ss	area under the steady state dose concentration-time curve over dosing interval tau
BLQ	below the limit of quantification
BLRM	Bayesian logistic regression model
BOR	best overall response
BP	blood pressure
bpm	beats per minute
bSAP	biomarker statistical analysis plan
CDISC	clinical data interchange standards consortium
CI	confidence interval
CL	total clearance of drug from eg, plasma
C max	maximum observed concentration
COVID	corona virus disease
CR	complete response
CRF	case report form
CRS	cytokine release syndrome
CSR	clinical study report
CT	computed tomography/clinical trial
CTCAE	common terminology criteria for adverse events
ctDNA	circulating tumor DNA
DC	disease control
DCR	disease control rate
DDI	drug-drug interaction
DLRM	dose level review meeting
DLT	dose-limiting toxicity
DOR	duration of response
ECG	electrocardiogram
EWOC	escalation with overdose control
FIH	first in human
HR	heart rate
ITT	intention to treat
LLQ	lower limit of quantification
MAP	meta-analytic-predictive
MedDRA	medical dictionary for regulatory activities
mg	milligrams
mITT	modified-intent-to-treat
mm	millimeters
MRI	magnetic resonance imaging
msec	millisecond
MTD	maximum tolerated dose
NC	not calculated
NCI	national Cancer Institute

---

Abbreviation	Term
ND	not done
NE	not evaluable
NS	no sample
NSCLC	non-small cell lung cancer
OR	overall response
ORR	objective response rate
OS	overall survival
PD	pharmacodynamics(s)/progressive disease
PDS	Pfizer data standard
PFS	progression-free survival
PK	pharmacokinetic(s)
PR	partial response
QTc	corrected QT
QTcF	QTc corrected QT (Fridericia method) using Fridericia's formula
R ac	accumulation ratio based on AUC (observed)
RECIST	response evaluation criteria in solid tumors
RP2D	recommended Phase 2 dose
SAE	serious adverse event
SAP	statistical analysis plan
SD	stable disease
t ½	terminal phase half-life
TEAE	treatment emergent adverse events
T max	time to reach C max
TTP	time to progression

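### In primed cohorts the accumulation ratio divides a full-dose AUC by a priming-dose AUC, so it mixes the dose step with accumulation

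*Protocol*

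**What the plan says.** Protocol 9.3.3 derives single- and multiple-dose parameters by noncompartmental analysis of concentrations "within a dose interval after Cycle 1 Day 1 and Cycle 2 Day 1". The sentence beginning "Multiple dose PK parameters to be estimated will include" ends with Rac, to be estimated where the data allow and defined as AUCss,tau divided by AUCsd,tau. Protocol Appendix 17 defines the denominator as the "area under the concentration-time curve after single dose over dosing interval", without dose normalization. SAP 3.2 and 6.2.2 repeat this text, and SAP Appendix 3 describes Rac as an observed, AUC-based ratio. One formula serves all regimens.

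For primed regimens the notes to Protocol Table 3 state "C1D1 is priming dose and C1D15 is full/maintenance dose", so C2D1 and later doses are full doses. A second priming dose on C1D8 is an option. Protocol 4.3.2 gives a "starting full dose that is 100% higher than the priming dose". Section 4.1 instead caps the starting full dose at the level where the CRS occurred, with priming one level below it. Both sections then allow the full dose to rise up to three-fold per step.

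Dose normalization is planned only for the plots of AUC and Cmax against dose.

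**The concern.** An accumulation ratio is meant to show how much exposure builds up under repeated dosing at a constant dose. Here the numerator follows full doses and the denominator follows a smaller priming dose, so a primed cohort would show a high Rac even with no accumulation. Rac is summarized by dose level. If the priming dose were held while the full dose rose, Rac would climb with dose and could be misread as dose-dependent accumulation. It also could not be compared with unprimed cohorts.

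Two-step priming adds a second mismatch. The first interval then lasts 7 days, so a 14-day single-dose AUC is never observed.

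**Working it through.** The documents give no numerical Rac to reproduce. The check uses one-compartment SC superposition.

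**Inputs**
- Linear PK and a 15-day half-life (Protocol 2.2.2): k = ln 2 / 360 h = 0.001925 per h.
- Q2W dosing (Protocol 6.1.1.2): tau = 336 h.
- Absorption rate ka = 0.019 per h. This is an assumption; the documents give none. It reproduces the single-dose Cmax of 9.2 ng/mL in Protocol 4.3.1.1: 100,000 ng × 0.70 / (84 mL/kg × 70 kg) = 11.9 ng/mL, times the peak factor (ka/k)^(−k/(ka−k)) = 0.7725, gives 9.2.
- r = full dose / priming dose. Section 4.3.2 gives r = 2 at the start. One-level steps in Table 8 give 100/60 = 1.67, 300/100 = 3 and 900/300 = 3.

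**Formulas**

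The AUC from 0 to T after one unit dose is proportional to G(T) = ka/(ka−k) × [(1−e^(−kT))/k − (1−e^(−ka·T))/ka]. Relative to the first 14-day interval, one dose contributes 1, 0.664, 0.348, 0.182 and 0.095 in intervals 1 to 5.

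With a first dose of 1 unit and later doses of r units:
- Rac at C2D1 (third dose) = r(1 + 0.664) + 0.348
- Rac at C3D1 (fifth dose) = r(1 + 0.664 + 0.348 + 0.182) + 0.095 = 2.195r + 0.095
- Rac at steady state = 2.40r

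**Results**

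| | C2D1 | C3D1 | Steady state |
|---|---|---|---|
| Unprimed (r = 1) | 2.01 | 2.29 | 2.40 |
| Primed, r = 2 | 3.68 | 4.49 | 4.79 |
| Primed, r = 3 | 5.34 | 6.68 | 7.19 |
| r = 2, each AUC divided by its dose | 1.84 | 2.24 | 2.40 |
| r = 3, each AUC divided by its dose | 1.78 | 2.23 | 2.40 |

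The inflation over the unprimed value is about 1.8 and 2.7 at C2D1, and 1.96 and 2.92 at C3D1. It is exactly 2 and 3 at steady state.

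The dose-normalized ratio is 9% and 12% low at C2D1 (1.84/2.01 and 1.78/2.01), because carry-over from the smaller priming dose remains. At C3D1 it is 2% to 3% low (2.24/2.29 and 2.23/2.29).

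**Sensitivity**
- With k = CL/Vss = 0.2/84 per h (half-life 12.1 days) and ka = 0.0236 per h, C3D1 gives 3.87 and 5.77 against 1.96 unprimed.
- With absorption ignored, a fraction q = 2^(−14/15) = 0.524 carries over per interval. C2D1 then gives r(1+q)+q² = 3.32 and 4.85, against 1.80 unprimed.

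**Which interval is available**

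In Table 4 the Cycle 2 code appears only at the Day 1 pre-dose PK sample. The Cycle 3 code appears at pre-dose, 4 h, 8 h, 168 h and the Day 15 pre-dose sample. The C2D1 interval named in 9.3.3 therefore has no scheduled post-dose profile, whereas C3D1 does.

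**The case against.** The strongest reply is that little rides on Rac. It is estimated only where data allow, priming is conditional, and Part 1 cohorts have about 3 participants. SAP 5.3.4 summarizes a parameter only with at least 3 evaluable values. The Part 2 PK endpoint is concentrations at selected times. All of this stands and limits the weight of the point.

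Three stronger readings may tempt a reader:
- *A distorted Rac would mislead dose or interval selection.* The documents do not support this. Protocol 4.3.4 rests Q2W on the projected half-life, and escalation uses the BLRM with the totality of data. No stated rule uses Rac.
- *The inflation always equals the dose ratio.* That holds only at steady state. At C2D1 it is smaller.
- *Values near 20 are to be expected.* A ratio of 9 gives 2.195 × 9 + 0.095 = 19.8 at C3D1. It requires, for example, a 100 µg priming dose held fixed while the full dose reaches 900 µg. That is an assumption, since Section 4.1 also allows other priming dose levels.

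It can also be said that SAP 5.3.4 already copes: underivable parameters are coded as not calculated, and an individual's known biased estimate is left out of summaries. The first provision may catch two-step priming, although the plan does not say so. The second cites a dosing error in one participant. Applied here it would remove Rac for whole primed cohorts and put nothing in its place.

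**Conclusion.** The point holds. As written, Rac in primed cohorts is not an accumulation ratio, and no text in either document corrects it. For full-to-priming ratios of 2 and 3 it would read about 3.7 and 5.3 at C2D1 against 2.0 unprimed, and about 4.5 and 6.7 at C3D1 against 2.3. These values assume linear PK, a 15-day half-life, Q2W dosing and ka of 0.019 per h. The direction does not depend on ka, and the steady-state inflation equals the dose ratio under linear PK.

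The consequence is confined to the interpretation of a descriptive secondary PK parameter if priming is used. It merits a short correction, not a design change.

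**What to change.** In Protocol 9.3.3 and SAP 3.2 and 6.2.2:
- For single-step primed participants, define Rac = (AUCss,tau / full dose) / (AUCsd,tau / priming dose), take AUCss,tau from the C3D1 profile, and state that linear PK is assumed. Compare with unprimed cohorts at the same cycle.
- Do not substitute the C1D15 interval as an uncorrected denominator. It carries priming-dose exposure and biases Rac low: with absorption ignored, 1.66 (r = 2) and 1.79 (r = 3) against 2.10 at steady state.
- For two-step priming, report Rac as not calculated, or take accumulation from the population PK model if it is run. Protocol 9.3.6.2 makes that model optional.

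Separately, Sections 4.1 and 4.3.2 describe the starting full dose differently. They must be reconciled, because the dose ratio depends on it.

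The cost of the Rac change is a sentence or two in each document and no new samples. The remaining limitation is the reliance on linear PK, which the protocol projects but has not yet observed in humans.

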9.3.4. Tertiary/Exploratory Endpoint(s)

Part 1

Efficacy Analysis

Response Evaluable Set will be used for ORR and PFS (RECIST). Tumor response will be presented in the form of participant data listings that include, but are not limited to tumor type, tumor response at each visit, and best overall response.

Data will be summarized (also graphically where appropriate) and listed by dose level.

Part 1 and 2

Analysis of Pharmacodynamics

Results of exploratory endpoint analyses will be described in the CSR to the extent possible. Due to the exploratory nature of the endpoints, the associated data analyses may not be complete at the time of CSR preparation. If results of exploratory endpoint analyses cannot be included in the CSR, they will be disseminated to the scientific community to the extent possible through presentation at scientific meetings and/or publication in peer-reviewed scientific journals.

9.3.5. Other Safety Analyses

All safety analyses will be performed on the safety population.

AEs, ECGs, BP, pulse rate, cardiac monitoring results, and safety laboratory data will be reviewed and summarized on an ongoing basis during the study to evaluate the safety of participants. Any clinical laboratory, ECG, BP, and PR abnormalities of potential clinical concern will be described. Safety data will be presented in tabular and/or graphical format and summarized descriptively, where appropriate.

Medical history and physical examination and neurological examination information, as applicable, collected during the course of the study will be considered source data and will not be required to be reported, unless otherwise noted. However, any untoward findings identified on physical and/or neurological examinations conducted during the active collection period will be captured as AEs if those findings meet the definition of an AE. Data collected at screening that are used for inclusion/exclusion criteria, such as laboratory data, ECGs, and vital signs, will be considered source data, and will not be required to be reported, unless otherwise noted. Demographic data collected at screening will be reported.

9.3.5.1. Electrocardiogram Analyses

Changes from baseline for the ECG parameters QT interval, heart rate, QTcF, PR interval, and QRS complex will be summarized by treatment and time.

The number (%) of participants with maximum postdose QTcF values and maximum increases from baseline in the following categories will be tabulated by treatment:

Safety QTcF Assessment

Degree of Prolongation	Mild (ms)	Moderate (ms)	Severe (ms)
Absolute value	>450-480	>480-500	>500
Increase from baseline		30-60	>60

If more than 1 ECG is collected at a nominal time after dose administration (for example, triplicate ECGs), the mean of the replicate measurements will be used to represent a single observation at that time point. If any of the 3 individual ECG tracings has a QTcF value >500 ms, but the mean of the triplicates is not >500 ms, the data from the participant's individual tracing will be described in a safety section of the CSR in order to place the >500 ms value in appropriate clinical context. However, values from individual tracings within triplicate measurements that are >500 ms will not be included in the categorical analysis unless the average from the triplicate measurements is also >500 ms. Changes from baseline will be defined as the change between the postdose QTcF value and the average of the time-matched baseline triplicate values on Day -1, or the average of the predose triplicate values on Day 1.

In addition, an attempt will be made to explore and characterize the relationship between plasma concentration and QT interval length using a PK/pharmacodynamics modeling approach. If a PK/pharmacodynamics relationship is found, the impact of participant factors (covariates) on the relationship will be examined.

The analysis of ECG results will be based on participants in the safety analysis set with baseline (pre-dose on Cycle 1 Day 1) and on-treatment ECG data.

ECG measurements (an average of the triplicate measurements) will be used for the statistical analysis and all data presentations. Any data obtained from ECGs repeated for safety reasons after the nominal time points will not be averaged along with the preceding triplicates. Interval measurements from repeated ECGs will be included in the outlier analysis (categorical analysis) as individual values obtained at unscheduled time points.

QT intervals will be corrected for HR using standard correction factors (ie, Fridericia's (default correction), Bazett's, and possibly a study-specific factor, as appropriate). Data will be summarized and listed for QT, HR, RR, PR, QRS, QTcF (and other correction factors, eg, QTcB as appropriate), and by study treatment (ie, monotherapy versus combination therapy) and dose. Individual QT (all evaluated corrections) intervals will be listed by study treatment, time, and dose. The most appropriate correction factor will be selected and used for the following analyses of central tendency and outliers and used for the study conclusions. Descriptive statistics (n, mean, median, standard deviation, minimum, and maximum) will be used to summarize the absolute corrected QT interval and changes from baseline in corrected QT after treatment by study treatment, dose, and time point. Details of additional analysis (if any) will be specified in SAP.

